3.6 Stopping/Pausing Guidelines

NP swabs will be analyzed in batches on a rolling basis throughout the study. At least one interim analysis will be performed based on the number of RT-PCR or culture confirmed influenza cases accrued at the time of the first interim analysis. After periodic review of safety and efficacy data, the DMC will make a recommendation as to whether enrolment in the study should continue, be stopped or paused.

Independent of the DMC, the Sponsor can halt the study at any time. If the study is halted, the Sponsor or delegate will promptly notify the health authorities and investigators, who will promptly inform the study subjects and local Ethics Committee/ Institutional Review Board (EC/IRB) as per local regulations. Study vaccinations and further enrolment will only occur after written authorization is provided by the Sponsor in conjunction with a recommendation to proceed by the DMC and in consultation with the health authorities and EC/IRB, as appropriate.

There are no predetermined stopping rules other than circumstances for which subjects may not be eligible for additional study vaccinations as described in [section 4, Selection of Study Population](#) or may be withdrawn from the study according to the best interests of the subject as described in [Section 3.8, Premature Withdrawal from Study](#).

3.7 Data Monitoring Committee

A DMC will be constituted for this trial. The members of the DMC shall have no involvement in the design or conduct of the trial and no financial interest in the outcome of the trial. The DMC will comprise solely of non-Seqirus employees, and include medical experts and a biostatistician. DMC will provide recommendation on stopping the study for either efficacy or futility after unblinded review of efficacy data in a pre-planned interim analysis. In addition, the DMC will monitor study progress and ensure the safety of subjects on an ongoing basis during the trial.

Primary efficacy endpoint.

Unblinded interim analyses for efficacy and futility will be executed by the DMC, after the majority of cases for the second season have been collected, and after observing at least 50% of planned events meeting the co-primary endpoint. In addition, the DMC will also review blinded, and if requested, semi-or fully-unblinded safety data at pre-specified intervals during the study. Another interim analysis might be recommended before target 381 cases are observed. Any unblinded data will be reviewed in closed sessions of the DMC, without participation of the Sponsor. All descriptions of these closed sessions will be unavailable to the Sponsor until study unblinding has occurred. All reports, following open sessions of blinded data review will be available to the Sponsor as appropriate. DMC recommendations will be expressed clearly to the Sponsor, at minimum in written communication.

After reviewing safety and efficacy data, the DMC will recommend that enrolment be continued, halted temporarily (pending additional information from the Sponsor or modification to the study design) or halted permanently as specified in the DMC charter.

The DMC charter will be written to clearly describe the operational processes and the roles and responsibilities, including the timing of meetings, methods of providing information to and from the DMC, format and content of data to be reviewed, frequency and format of meetings, and membership requirements.

3.8 Premature Withdrawal from Study

Subjects may withdraw at any time, or be dropped from the study at the discretion of the investigator should any untoward effects occur and/or for safety reasons. In addition, a subject may be withdrawn by the investigator or the Sponsor if he/she violates the study protocol and related procedures or for administrative reasons. The investigator or study coordinator must notify the Sponsor immediately when a subject has been withdrawn due to an adverse event.

The circumstances above are referred to as premature withdrawal from the study, and the reason for premature withdrawal should be clearly documented and detailed in the source documentation. The investigator should make every attempt to evaluate the subject's safety, including resolution of ongoing AEs, at the time of premature withdrawal. If a subject want to withdraw from the study before all doses are administered or prior to the last planned study visit, the subject will be asked to be followed for safety for the duration of the study. When a subject withdraws, or is withdrawn, from the study, the procedures described in [section 5.5.1, Early Termination Visit](#) should be completed if possible.

The reasons for premature withdrawal from the study include:

- Adverse event,
- Death
- Withdrawal of consent
- Lost to follow-up
- Administrative reason
- Protocol deviation
- Other

These reasons are described in greater detail below.

Adverse Event

For any subject withdrawn from study participation prior to the planned Study Termination Visit, it is important to determine if an AE was associated with the reason for discontinuing the study. This AE must be identified on the AE CRF page by indicating "Withdrawn from study due to AE". Any ongoing AEs at the time of study withdrawal must be followed until resolution or stabilization.

Subjects who develop a serious adverse event (SAE) judged to be possibly or probably related to the study vaccine, including hypersensitivity reactions, should not receive subsequent vaccination.

If a medically attended adverse event occurred within 30 days following a primary protocol definition of ILI, the event should also be reported on the AE eCRF page.

Death

For any subject withdrawn from study participation due to death, this should be noted on the Study Termination CRF page and the associated SAE that led to the death must be reported.

Withdrawal of consent

The subject and/or parent(s)/legal guardian(s) can withdraw consent for participation in the study at any time without penalty or loss of benefit to which the subject is otherwise entitled. Reason for early termination should be deemed as “withdrawal of consent” if the subject withdraws from participation due to a non-medical reason (i.e., reason other than AE). If the subject and/or parent(s)/legal guardian(s) intends to withdraw consent from the study, the investigator should clarify if the subject will withdraw completely from the study or if the subject will continue study participation for safety, or a subset of other study procedures. If the subject requests complete withdrawal from the study, no further study interventions will be performed with the subject.

In countries where the Health Insurance Portability and Accountability Act (HIPAA) is applicable, if a subject and/or parent(s)/legal guardian(s) withdraws consent but does not revoke the HIPAA authorization, the Sponsor will have full access to the subject’s medical records, including termination visit information. If a subject and/or parent(s)/legal guardian(s) revokes only the HIPAA authorization, the Sponsor will have full access to all of the subject’s medical records prior to the date and time of written revocation.

Lost to Follow-Up

For subjects who fail to show up for final visits (clinic or telephone contacts), or for three consecutive visits (clinic or (safety or diary) telephone contacts), study staff are encouraged to make at least three documented attempts to contact the subject by telephone and at least one documented written attempt to contact the subject and/or parent(s)/legal guardian(s) to encourage the completion of study termination procedures. These efforts to contact the subject should be recorded in the source document. The termination date for the subject to be captured on the Study Termination CRF page is the date of the last successful contact (visit or telephone) with the subject.

Administrative Reason

Examples for subjects withdrawn from the study due to administrative reason can include: Sponsor decision to terminate the study, subject meeting a pre-specified withdrawal criterion, subject discontinuation for insurance issues, moving, no time, etc. This reason

should be noted in the Study Termination CRF page and any ongoing AEs at the time of study withdrawal must be followed until resolution/stabilization.

If the clinical study is prematurely terminated by the Sponsor, the investigator is to promptly inform the study subjects and local EC/IRB and should assure appropriate therapy and follow up for the subjects. All procedures and requirements pertaining to the archiving of study documents should be followed. All other study materials (study medication/vaccines, etc.) must be returned to the Sponsor.

For subjects who are withdrawn from the study due to receipt of an excluded medication/vaccination or due to significant protocol non-compliance, this reason should be noted in the Study Termination CRF page. A subject (or legal guardian) is considered to be compliant if the Investigator judges that the subject will complete the Subject Diary when applicable, return for all the follow-up visits, and be available for telephone calls as scheduled.

Protocol Deviation

A protocol deviation is any change, divergence, or departure from the study design or procedures of a study protocol. In general, subjects associated with protocol deviations may remain in the study unless continuation in the study jeopardizes the subject's health, safety, or rights.

Investigators will apply due diligence to avoid protocol deviations. Under no circumstances should the investigator contact Seqirus or its agents, if any, monitoring the study to request approval of a protocol deviation, as no authorized deviations are permitted. If the investigator feels a change to the protocol would improve the conduct of the study this must be considered a protocol amendment, and unless such an amendment is agreed upon by Seqirus and approved by the IRB/EC and health authorities it cannot be implemented.

Any subject who becomes pregnant during the study, despite the protocol requirement for adequate contraception, will not receive further vaccination(s) but should be encouraged to continue participating in the study for safety follow-up. The site must complete a paper Pregnancy Report form (initial report) as soon as possible after learning of pregnancy occurrence (see [section 7.1.6, Pregnancies](#) for further details). If the pregnant subject withdraws from the study for any of the above categories except death, the site will obtain permission from the subject to continue to remain in contact with her until the outcome of the pregnancy is known, even if the outcome is not known until after the subject reaches the end of follow-up period.

3.9 End of Study

Evaluation of the primary and secondary efficacy objectives requires the testing of biological samples from the study subjects, which can only be completed after all samples are collected. Nasopharyngeal swabs may be collected up to end of influenza season. For the purpose of this protocol, end of study is defined as the completion of the testing of such biological samples, to be achieved no later than 8 months after LSLV.

4. SELECTION OF STUDY POPULATION

4.1 Inclusion Criteria

In order to participate in this study, all subjects must meet ALL of the inclusion criteria described.

1. Males or females ≥ 2 years to < 18 years of age on the day of first study vaccination;
2. Individual has and/or has (a) parent(s) or legal guardian(s) who has/have given informed consent/assent after the nature of the study has been explained in accordance with the practices described in protocol [Section 5.1.1.](#) and according to local regulatory requirements;
3. If the individual is of an age where, according to local regulations, informed assent is required, that individual has provided assent to participate in the study.
4. Individual and individual's parent or legal guardian can comply with study procedures and are available for follow-up;
5. Individual is in generally good health as per the Investigator's medical judgement;

4.2 Exclusion Criteria

Each subject must not have:

1. Individual with clinical signs of fever and/or an oral temperature of $\geq 100.4^{\circ}\text{F}$ (38.0°C) within three days prior to vaccination;
2. Individuals with a known history of any anaphylaxis, serious vaccine reactions or hypersensitivity to any of the vaccine components described in investigator brochure, or having any of the contraindications listed in the package insert of the comparator vaccine;
3. Individuals with history of Guillain-Barré syndrome or other demyelinating diseases such as encephalomyelitis and transverse myelitis;

4. Female subject “of childbearing potential¹”, sexually active, and not used any of the “acceptable contraceptive method²” for at least 2 months prior to study entry and intend to use until the end of subject participation;
5. Individual is pregnant or breast feeding female;
6. Individual and/or individual’ parent/guardians who are not able to comprehend or follow all required study procedures for the whole period of the study;
7. Individual has received prior Meningococcal ACWY vaccination that conflicts with national recommendations or local practices for timing of primary or booster vaccination
8. Individual has received influenza vaccination or has had documented influenza disease in the last 6 months;
9. Known or suspected congenital or acquired immunodeficiency; or receipt immunosuppressive therapy, such as anti-cancer chemotherapy or radiation therapy, within the preceding 6 months; or systemic corticosteroid therapy (prednisone or equivalent) at any dose for more than 2 consecutive weeks (14 days) within the past 3months. Topical, inhaled and intranasal corticosteroids are permitted. Intermittent use (one dose in 30 days) of intra-articular corticosteroids is also permitted;
10. Administration of immunoglobulin and/or any blood products within the 3 months preceding vaccination, or planned administration during the study;
11. Individual has participated in any clinical trial with another investigational product 30 days prior to first study visit or intent to participate in another clinical study at any time during the conduct of this study. Concomitant participation in an observational study (not involving drugs, vaccines, or medical devices) is acceptable;
12. Medical conditions or treatments contraindicating intramuscular vaccination due to increased risk of bleeding. These may include known bleeding disorders (such as thrombocytopenia), or treatment with anticoagulants (such as warfarin) in the 3

¹ A female is considered to be of childbearing potential if post onset of menarche and before natural or induced menopause. Natural menopause is recognized to have occurred after 12 consecutive months of amenorrhea for which there is no other obvious pathological or physiological cause. Induced menopause is recognized to have occurred after hysterectomy, after bilateral oophorectomy, or iatrogenic ablation of ovarian function.

² The following birth control methods are considered effective:

- Abstinence
- Hormonal contraceptive (such as oral, injection, transdermal patch, implant)
- Diaphragm with spermicide, tubal occlusion device
- Intrauterine device (IUD)
- Tubal ligation
- Male partner using condom
- Male partner having been vasectomized

- weeks preceding vaccination. However, antiplatelet agents such as low-dose aspirin, ticlopidine (Ticlid) and clopidogrel (Plavix) are permitted;
13. Evidence, or history (within the previous 12 months) of drug or alcohol abuse;
 14. Study personnel or immediate family members (brother, sister, child, parent), the spouse of study personnel or individuals who are financially or emotionally dependent on study staff
 15. Participation in this trial in a prior season, if applicable.
 16. Any clinical condition that, in the opinion of the investigator, might interfere with the results of the study or pose additional risk to the subject due to participation in the study

Prior to receipt of study vaccination, subjects must be evaluated to confirm that they are eligible for subsequent vaccination. If subjects do not meet any of the original inclusion criteria listed above, they should not receive additional vaccinations.

4.3 Criteria for Delay of Vaccination

There may be instances when individuals meet all eligibility criteria for vaccination yet have a transient clinical circumstance which may warrant delay of vaccination: body temperature elevation [$\geq 38.0^{\circ}\text{C}$ ($\geq 100.4^{\circ}\text{F}$) within 3 days prior to intended study vaccination], or use of antipyretics and/or analgesic medications within 24 hours prior to vaccination. Under such circumstances, a subject may be considered eligible for study enrolment after the appropriate window for delay of vaccination has passed and inclusion/exclusion criteria have been rechecked, and if the subject is confirmed to be eligible.

4.4 Criteria for Repeat Vaccination in the Study

Prior to receipt of second study vaccination (“not previously vaccinated” subjects), subjects must be evaluated to confirm that they are eligible for subsequent vaccination. If subjects meet any of the original exclusion criteria (except for those listed under [Section 4.3](#)) or the criteria listed below, they should not receive additional vaccinations.

- Subjects who experience any SAE judged to be related to study vaccine including hypersensitivity reactions.
- Subjects who develop any new condition which, in the opinion of the investigator, may pose additional risk to the subject if he/she continues to participate in the study.

Subjects who meet any of these criteria must not receive further study vaccinations. However, these subjects should be encouraged to continue study participation, as discussed in [Section 3.6](#).

There are also circumstances under which repeat vaccination is a contraindication in this study. These circumstances include anaphylaxis or severe hypersensitivity reactions following vaccination. If these reactions are to occur, the subject must not receive additional vaccinations but is encouraged to continue in study participation.

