review of prior and concomitant medications/vaccinations, and confirmation of subject eligibility (including pregnancy testing for female subjects of childbearing potential), subjects will be enrolled into the study and randomized via an interactive response technology (IRT) system to receive QIVc or US licensed non-influenza comparator vaccine. Randomized subjects will be stratified in two age cohorts: ≥ 2 years to < 9 years of age and ≥ 9 years to < 18 years of age. Subjects between ≥ 2 to < 9 years of age will be stratified by previous influenza vaccine status as “previously vaccinated” and “not previously vaccinated”.

“Previously vaccinated” subjects are defined as any child 9 years of age and older, and any child under the age of 9 years who has received 2 or more doses of seasonal influenza vaccine before or during the last influenza season. The two previous doses need not have been given during the same season or consecutive seasons. “not previously vaccinated” subjects are defined as any child under the age of 9 years who did not receive 2 or more doses of seasonal influenza vaccine before or during the last influenza season and any child under the age of 9 years with unknown influenza vaccination history.

Subjects ≥ 2 to < 9 years of age who are “not previously vaccinated” will receive two (2) vaccinations separated by approximately 28 days. Subjects ≥ 2 to < 9 years of age who are “previously vaccinated” and subjects ≥ 9 to < 18 years of age will receive one (1) vaccination. A subset of subjects ≥ 2 to < 9 years of age will be selected to participate in an assessment of immunogenicity, balanced by vaccination status and assigned vaccination allocation. Solicited adverse events will be collected for all subjects.

After randomization, all subjects will receive a dose of 0.5 mL of study vaccine to which they were assigned (QIVc or non-influenza comparator vaccine) on Day 1, administered intramuscularly in the deltoid muscle, preferably of the non-dominant arm. For those subjects who are “not previously vaccinated” a second administration will follow on Day 29, as presented below:

Subjects	QIVc Group	Comparator Group
“previously vaccinated” ≥ 2 years to < 9 years of age, and ≥ 9 years to < 18 years of age	Day 1: QIVc	Day 1: Men ACWY
“not previously vaccinated” ≥ 2 years to < 9 years of age	Day 1: QIVc Day 29: QIVc	Day 1: Men ACWY Day 29: Saline

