7. Take body temperature (preferably oral). If the body temperature is $\geq 38.0^{\circ}\text{C}$ ($\geq 100.4^{\circ}\text{F}$), vaccination must be postponed until three days after the fever has

resolved. Vaccination is also postponed for any clinically significant active infection based on investigator's clinical judgment ([see section 4.3](#)).

8. The use of any analgesics (oral, topical, etc.) and/or antipyretics within 24 hours prior to vaccination is an exclusion criteria ([see section 6.5](#)). Use of these medications can decrease the immune response to the vaccination. Verify that the subject has not applied topical analgesic/anesthetic to the anticipated injection site within the past 24 hours, as application of analgesic/anesthetic patch/cream may interfere with the ability to interpret local reactions after vaccination. If topical analgesic/anesthetic has been applied to the area to be injected, the opposite limb that has not been treated with analgesic/anesthetic may be injected. If subject took oral antipyretics and/or analgesic medications within 24 hours prior to vaccination, document this and the reason for their use (prophylaxis versus treatment) in the subject's source record and eCRF.

Prior to receipt of second study vaccination ("not previously vaccinated" children), subjects must be evaluated to confirm that they are eligible for subsequent vaccination. If subjects meet any of the original exclusion criteria (except for those listed under [section 4.3](#)) or meet any of the criteria listed under [section 4.4](#) they should not receive additional vaccinations.

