- Blood, blood products and/or plasma derivatives or any parenteral immunoglobulin preparation.
-
- Any non-study investigative agents.

A non-study influenza vaccination(s) is considered a protocol deviation if received from Day 1 until the end of season or Day 181/ 209 whichever comes first and may result in the subject being excluded from the Per Protocol Set (PPS).

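### The Day 29 re-check does not exempt exclusion 8, so as written it contradicts the second QIVc dose and leaves influenza documented since Day 1 to each site's reading

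*Protocol*

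**What the plan says.** Children aged 2 to under 9 years who are not previously vaccinated "will receive two (2) vaccinations separated by approximately 28 days" (Protocol 3.1). For the QIVc arm the schedule table reads "Day 1: QIVc Day 29: QIVc". Comparator children receive Men ACWY on Day 1 and saline on Day 29.

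Protocol 4.4 requires an eligibility check before the second injection. "If subjects meet any of the original exclusion criteria", apart from those in Section 4.3, or either of two further criteria, they are not to be vaccinated again. The same section later restates this as a must-not. Protocol 5.2.2 repeats the rule with the same single carve-out: "If subjects meet any of the original exclusion criteria (except for those listed under" Section 4.3.

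Section 4.3 covers children who are otherwise eligible "yet have a transient clinical circumstance which may warrant delay of vaccination: body temperature elevation" within the preceding three days, or "use of antipyretics and/or analgesic medications within 24 hours prior to vaccination". It lists nothing else.

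Exclusion 8 in Protocol 4.2 reads: "Individual has received influenza vaccination or has had documented influenza disease in the last 6 months". It carries no qualifier for the study's own vaccine and is not confined to the first visit. Protocol 6.5, by contrast, does add the qualifier when it means outside product: "A non-study influenza vaccination(s) is considered a protocol deviation if received from Day 1".

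**The concern.** Exclusion 8 has two legs, and each causes trouble when it is re-applied at Day 29.

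**Vaccination leg.** QIVc is an influenza vaccine given about 28 days earlier, well inside the six-month look-back. The re-check therefore rules out the dose that the schedule prescribes, and only in the QIVc arm. A site cannot satisfy both texts, and Protocol 3.8 says that no deviation may be authorised. The leg also cannot be applied blind, because whether a child meets it depends on the Day 1 allocation.

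**Disease leg.** A child with influenza documented after Day 1 meets exclusion 8 in either arm. Receipt of the second injection then depends on an outcome that the vaccine is meant to prevent. The injection at issue is active vaccine in one arm and saline in the other. Two sites reading the same text could treat the same child differently, and the choice carries into the case window for the primary endpoint and into the per-protocol set.

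**Working it through.** The plan gives no figure to reproduce. The check sets the passages side by side and adds simple arithmetic.

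1. **Is exclusion 8 exempt at Day 29?** The carve-out in 4.4 and 5.2.2 points only to 4.3, which lists recent fever and antipyretic or analgesic use. Exclusion 8 is not there. Table 5 marks the inclusion/exclusion row for Day 1 only, but 4.4, 5.2.2 and 5.2.3 expressly require eligibility to be confirmed again before the second injection.

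2. **Who meets the vaccination leg if it is read literally?** Every two-dose QIVc child who had the Day 1 dose, and no comparator child by virtue of study vaccine. Table 3.1.1 plans 1,022 to 1,430 such QIVc children out of 3,846 in the arm:
   - 1,022 / 3,846 = 26.6%
   - 1,430 / 3,846 = 37.2%

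   This is the reach of the wording, not an expected number of withheld doses.

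3. **Can blinded staff apply it?** Under Protocol 3.3 the staff who give the injections are unblinded and take no part in data collection after vaccination, so the Day 29 assessments fall to blinded staff. They can screen for outside influenza vaccine, but cannot judge whether the Day 1 injection was an influenza vaccine.

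4. **Who meets the disease leg?** A child in either arm whose influenza is documented by Day 29. Surveillance runs from Day 1 (Protocol 5.3.3), and influenza-like symptoms are assessed again just before the second injection (5.2.2, item 5). Swabs go to a central laboratory (3.1) and are tested in batches (3.6), so some illnesses would not yet be documented.

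5. **What follows for the primary endpoint?** Cases count from more than 14 days after the last vaccination (Protocol 8.1.1.2; SAP 2.1.2). The efficacy FAS needs only one dose (SAP 7.3). For onset on study day *d*:
   - Second injection given on Day 29: *d* − 29 > 14, so counting starts on Day 44.
   - Second injection withheld, last vaccination received on Day 1: *d* − 1 > 14, so counting starts on Day 16.

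   Take onset on Day 20, documented before Day 29. If the injection is given, the illness falls before Day 44 and is not a case. If it is withheld and the window runs from the dose received, the illness is 19 days after the last vaccination and is a primary event. The same holds for any onset from Day 16 to Day 28 (28 − 16 + 1 = 13 days).

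6. **Does any text settle the window?** Protocol 3.1 starts it from the second vaccination for these children but does not say what happens without one. SAP 7.3 places the last vaccination at Visit 2 or Visit 3. In Protocol Tables 3 and 5 those are the Day 22 and Day 50 visits, at which no vaccine is given, so that sentence does not settle it.

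7. **Per-protocol status.** The PPS requires the vaccine at the scheduled time points (Protocol 8.3.5; SAP 7.4). Neither document says whether a dose withheld under 4.4 breaks that condition.

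**The case against.** The strongest reply is that nobody would read the rule this way. The Day 29 QIVc dose is prescribed in the synopsis, in Protocol 3.1 and in SAP Section 3. Section 4.4 exists to govern repeat vaccination. Protocol 6.5 ties the six-month record of influenza vaccination to the period before enrolment and, from Day 1 on, treats only non-study influenza vaccine as a deviation. That stands as evidence of intent. It does not amend exclusion 8, and it does not reach the disease leg.

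A second reply is that withholding an injection after documented influenza is a coherent rule, and that the primary analysis uses the FAS as randomised, so these children are not lost. The first part is fair: the point here is not that either clinical choice is wrong. The FAS does not remove the difficulty, because the FAS case window moves with the second injection.

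A reader might infer four stronger things that the documents do not support:

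- **The QIVc arm becomes a one-dose arm.** This follows only from the literal text, against a schedule whose intent is clear.
- **Exclusion 7 creates a mirror problem for the comparator.** It applies only where prior Men ACWY conflicts with national recommendations or local practice, which are not in the documents, and comparator children receive saline on Day 29.
- **Any influenza after Day 1 triggers the bar.** Exclusion 8 requires documented disease.
- **The 8% attack rate gives a count of affected children.** The plan assumes that this risk lies entirely within follow-up, for an endpoint that starts after the last vaccination. It gives no share of cases for Days 1 to 28.

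**Conclusion.** The point holds in two parts of different weight.

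The vaccination leg is a contradiction between 4.2, 4.4 and 5.2.2 on one side and the vaccination schedule on the other. It covers the whole two-dose QIVc stratum (1,022 to 1,430 planned children) in wording only. It does not predict that doses would be withheld.

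The disease leg is a real gap. For a child with influenza documented between Day 1 and Day 29, the second injection, the date that starts the case window and PPS membership all depend on a post-randomisation outcome and on site interpretation. The documents do not allow the number of such children to be derived. It may be near 0 if both doses precede circulation, and batch testing limits how many cases are documented in time. The Day 16 versus Day 44 result assumes that the last vaccination means the last one received and that the second injection falls exactly on Day 29.

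A dosing-eligibility rule that contradicts the schedule should be corrected even though its numerical effect cannot be stated.

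**What to change.** - Reconcile exclusion 8 in Protocol 4.2, and Sections 4.4 and 5.2.2, with the Day 1/Day 29 schedule.
- Replace the general reference to the original exclusion criteria with a list, by name, of those re-applied at Day 29, worded so that blinded staff can apply each one without knowing the arm.
- State in one place how influenza documented since Day 1 is handled before the second injection. Which way it goes is the sponsor's clinical decision.
- State in the protocol and SAP endpoint definitions which date starts the >14-day window when no second injection is given, and say how such a child is classified for the PPS.

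The cost is wording in those protocol sections, matching sentences in the SAP and the corresponding eCRF eligibility check. It needs no additional subjects or visits.
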